5.1.1.3.1 Efficacy Endpoints

The primary efficacy endpoint is the change from baseline (CFB) to Week 6 in the percentage of catheterizations without a leaking accident as recorded in the 2-day urinary diary.

Distributions for the primary endpoint between participants treated with oxybutynin chloride gel in the two different types of treatment periods (Pre-Amendment 3 double-blind treatment period or Post-Amendment 3 open-label treatment period) of the study will be compared. Specifically, an exact two-sample Kolmogorov-Smirnov test will be used to compare the two distributions, with a p-value of 0.05 used as the threshold to reject the null hypothesis that the distributions for the two periods are the same.

If the distributions of the endpoint between these two periods are similar ($p \ge 0.05$), the primary analysis of the primary efficacy endpoint analysis will compare the difference between oxybutynin chloride gel and placebo in the Combined ITT population for the change from baseline in the percentage of catheterizations without a leaking accident at Week 6 using an analysis of covariance (ANCOVA) model with the baseline measure of the primary variable as the covariate and treatment group (active or placebo) as the factor.

If the distributions for the endpoint show a significant difference (p < 0.05) between these two periods, the data from the Pre-Amendment 3 double-blind treatment period and the data from the Post-Amendment 3 open-label treatment period will be analyzed separately as the primary analysis:

• For Pre-Amendment 3, the primary endpoint analysis will compare the difference between oxybutynin chloride gel and placebo in the Pre-Amendment 3 ITT population for the change from baseline in the percentage of catheterizations without a leaking accident at Week 6 using an ANCOVA model with the baseline measure of the primary variable as the covariate and treatment group as the factor.

SAP OG09002 Oxybutynin Chloride 10% Gel

• For Post-Amendment 3, a 2-sided one-sample t-test will be used on the primary endpoint to test for a significant difference from zero in the Post-Amendment 3 ITT population.

The analysis method which is not used as the primary analysis will serve as a supplementary analysis of the primary endpoint.

Secondary endpoints include the change from baseline to Week 6 of treatment in:

- average volume of urine collected per catheterization
- average volume of urine collected at first (morning awakening) catheterization
- average number of catheterizations per day

Analysis populations and methodologies for secondary endpoints will be handled similarly to the primary endpoint. For each secondary endpoint, an exact two-sample Kolmogorov-Smirnov test will be used to compare the two distributions, with a p-value of 0.05 used as the threshold to determine the main analysis method for that endpoint (i.e., the main analysis will use the combined ITT population if $p \ge 0.05$, and the main analysis will analyze the treatment periods separately if p < 0.05).

Efficacy variables will be analyzed as described in the following table. The urinary diary endpoints will be analyzed for the ITT and PP analysis populations at Week 6 (LOCF), and for ITT and PP analysis populations at each OC Visit. The pharmacodynamic endpoints will be analyzed for the ITT population.

Table 5-12 Efficacy and Pharmacodynamic Analyses

Endpoint	Description	Timing	Methodology
Percentage of	Change from baseline to Week 6 (or	Pre-Amendment 3	CFB ANCOVA Pre-
catheterizations without a	LOCF) calculated over 2 diary days	Week 6 (LOCF) of	Amendment 3; CFB
leaking accident		double-blind period;	one-sample t-test
		Post-Amendment 3	Post-Amendment 3;
		Week 6 (LOCF) of	CFB ANCOVA for
		open-label period;	Combined ITT
		Combined ITT	
		(LOCF)	
Percentage of	Raw value for Week 6 (or LOCF)	Pre-Amendment 3	Continuous
catheterizations without a	calculated over 2 diary days	Week 6 (LOCF) of	descriptives
leaking accident		double-blind period;	
		Post-Amendment 3	
		Week 6 (LOCF) of	
		open-label period	
Percentage of	Change from baseline to OC Visits	Pre-Amendment 3	CFB ANCOVA Pre-
catheterizations without a	(Week 2, Week 6) calculated over 2	Week 2, Week 6 of	Amendment 3; CFB
leaking accident	diary days	double-blind period;	one-sample t-test
		Post-Amendment 3	
		Week 6 of open-	

SAP OG09002 Oxybutynin Chloride 10% Gel

Endpoint	Description	Timing	Methodology
		label period; Combined ITT (OC)	Post-Amendment 3; CFB ANCOVA for Combined ITT
Percentage of catheterizations without a leaking accident	Raw value for OC Visits (Week 0, Week 2, Week 6) calculated over 2 diary days	Pre-Amendment 3 Week 0, Week 2, Week 6 of double- blind period; Post-Amendment 3 Week 0, Week 6 of open-label period	Continuous descriptives
Average volume of urine collected at first (morning awakening) catheterization	Average change from baseline to Week 6 (or LOCF) calculated over 2 diary days	Pre-Amendment 3 Week 6 (LOCF) of double-blind period; Post-Amendment 3 Week 6 (LOCF) of open-label period; Combined ITT (LOCF)	CFB ANCOVA Pre- Amendment 3; CFB one-sample t-test Post-Amendment 3; CFB ANCOVA for Combined ITT
Average volume of urine collected at first (morning awakening) catheterization	Average raw value for Week 6 (or LOCF) calculated over 2 diary days	Pre-Amendment 3 Week 6 (LOCF) of double-blind period; Post-Amendment 3 Week 6 (LOCF) of open-label period	Continuous descriptives
Average volume of urine collected at first (morning awakening) catheterization	Average change from baseline for OC Visits (Week 2, Week 6) calculated over 2 diary days	Pre-Amendment 3 Week 2, Week 6 of double-blind period; Post-Amendment 3 Week 6 of open- label period; Combined ITT (OC)	CFB ANCOVA Pre- Amendment 3; CFB one-sample t-test Post-Amendment 3; CFB ANCOVA for Combined ITT
Average volume of urine collected at first (morning awakening) catheterization	Average Raw value for OC Visits (Week 0, Week 2, Week 6) calculated over 2 diary days	Pre-Amendment 3 Week 0, Week 2, Week 6 of double- blind period; Post-Amendment 3 Week 0, Week 6 of open-label period	Continuous descriptives
Average number of catheterizations per day	Average change from baseline to Week 6 (or LOCF) calculated over 2 diary days	Pre-Amendment 3 Week 6 (LOCF) of double-blind period; Post-Amendment 3 Week 6 (LOCF) of open-label period; Combined ITT (LOCF)	CFB ANCOVA Pre- Amendment 3; CFB one-sample t-test Post-Amendment 3; ANCOVA for Combined ITT
Average number of catheterizations per day	Average raw value for Week 6 (or LOCF) calculated over 2 diary days	Pre-Amendment 3 Week 6 (LOCF) of double-blind period; Post-Amendment 3 Week 6 (LOCF) of open-label period	Continuous descriptives

SAP OG09002 Oxybutynin Chloride 10% Gel

Endpoint	Description	Timing	Methodology
Average number of catheterizations per day	Average change from baseline for OC Visits (Week 2, Week 6) calculated over 2 diary days	Pre-Amendment 3 Week 2, Week 6 of double-blind period; Post-Amendment 3 Week 6 of open- label period; Combined ITT (OC)	CFB ANCOVA Pre- Amendment 3; CFB one-sample t-test Post-Amendment 3; CFB ANCOVA for Combined ITT
Average number of catheterizations per day	Raw value for OC Visits (Week 0, Week 2, Week 6) calculated over 2 diary days	Pre-Amendment 3 Week 0, Week 2, Week 6 of double- blind period; Post-Amendment 3 Week 0, Week 6 of open-label period	Continuous descriptives
Average volume of urine collected per catheterization (for Pre-Amendment 3 population only)	Change from baseline to Week 6 (or LOCF) calculated over 2 diary days	Pre-Amendment 3 Week 6 (LOCF) of double-blind period	CFB ANCOVA Pre- Amendment 3
Average volume of urine collected per catheterization (for Pre-Amendment 3 population only)	Average raw value for Week 6 (or LOCF) calculated over 2 diary days	Pre-Amendment 3 Week 6 (LOCF) of double-blind period	Continuous descriptives
Average volume of urine collected per catheterization (for Pre-Amendment 3 population only)	Change from baseline for OC Visits (Week 2, Week 6) calculated over 2 diary days	Pre-Amendment 3 Week 2, Week 6 of double-blind period	CFB ANCOVA Pre- Amendment 3
Average volume of urine collected per catheterization (for Pre-Amendment 3 population only)	Average raw value for OC Visits (Week 2, Week 6) calculated over 2 diary days	Pre-Amendment 3 Week 0, Week 2, Week 6 of double- blind period	Continuous descriptives
Maximal bladder capacity	Change from baseline to Week 6 (or LOCF)	Pre-Amendment 3 Week 6 (LOCF) of double-blind period; Post-Amendment 3 Week 6 (LOCF) of open-label period; Combined ITT (LOCF)	CFB ANCOVA Pre- Amendment 3; CFB one-sample t-test Post-Amendment 3; CFB ANCOVA for Combined ITT
Detrusor pressure at maximal bladder capacity	Change from baseline to Week 6 (or LOCF)	Pre-Amendment 3 Week 6 (LOCF) of double-blind period; Post-Amendment 3 Week 6 (LOCF) of open-label period; Combined ITT (LOCF)	CFB ANCOVA Pre- Amendment 3; CFB one-sample t-test Post-Amendment 3; CFB ANCOVA for Combined ITT

SAP OG09002 Oxybutynin Chloride 10% Gel

Endpoint	Description	Timing	Methodology
Maximum amplitude of involuntary detrusor pressure	Change from baseline to Week 6 (or LOCF)	Pre-Amendment 3 Week 6 (LOCF) of double-blind period; Post-Amendment 3 Week 6 (LOCF) of open-label period; Combined ITT (LOCF)	CFB ANCOVA Pre- Amendment 3; CFB one-sample t-test Post-Amendment 3; CFB ANCOVA for Combined ITT
Volume at first involuntary detrusor contraction	Change from baseline to Week 6 (or LOCF)	Pre-Amendment 3 Week 6 (LOCF) of double-blind period; Post-Amendment 3 Week 6 (LOCF) of open-label period; Combined ITT (LOCF)	CFB ANCOVA Pre- Amendment 3; CFB one-sample t-test Post-Amendment 3; CFB ANCOVA for Combined ITT
Presence (versus total absence) of involuntary detrusor contractions at > 15 cm H2O	Raw value at Week 6 (or LOCF)	Pre-Amendment 3 Week 6 (LOCF) of double-blind period; Post-Amendment 3 Week 6 (LOCF) of open-label period; Combined ITT (LOCF)	CMH test Pre-Amendment 3; Exact 95% CI Post-Amendment 3; CMH test for Combined ITT

¹ Weeks are defined in Section 6.2.1.

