11.5.1 Statistical Analysis of the Primary Efficacy Endpoint

The primary efficacy *parameter is the CFB to Week 6 (or LOCF) in the percentage of catheterizations without a leaking accident. The primary efficacy parameter* will be analyzed using an analysis of covariance (ANCOVA) model with the baseline measure of the primary variable as the covariate and treatment group *and study part (Pre-Amendment 3 and Post-Amendment 3) as factors.*

To assess the effect of the study design, the primary efficacy parameter will be analyzed using a random effects mixed model using the combined data from the Pre-Amendment 3 doubleblind treatment period and the data from the Post-Amendment 3 open-label treatment period. The model will include the baseline measure and other baseline characteristics as covariates and treatment (Pre-Amendment 3 double-blind placebo, Pre-Amendment 3 double-blind oxybutynin chloride gel, Post-Amendment 3 open-label oxybutynin chloride gel) as factors and will account for the heterogeneity between parts of the study (Pre-Amendment 3 vs Post-Amendment 3) by using a random effect for study part. If the analyses indicate heterogeneity, the data from the Pre-Amendment 3 double-blind treatment period and the data from the Post-Amendment 3 open-label treatment period will be analyzed separately. For the Post-Amendment 3 ITT population, the significance of the change from baseline on the primary efficacy measure will be assessed from a 2-sided, 1-sample t-test. For the Pre-Amendment 3 ITT population the primary efficacy parameter will be analyzed using an ANCOVA model with the baseline measure of the primary variable as the covariate and treatment group as factors.

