5.1.1.6 Subgroup Analyses

The primary and secondary efficacy LOCF data analyses will be analyzed separately for each group for each ITT population, as appropriate:

Age Group:

- 3 to < 6 years
- 6 to < 12 years
- 12 to < 17 years

Weight Category by Age Group:

- \leq 18 kg and 3 to \leq 6 years
- >18 kg and 3 to < 6 years
- <=25 kg and 6 to < 12 years
- >25 kg and 6 to < 12 years
- <=50 kg and 12 to <17 years
- >50 kg and 12 to <17 years

Sex:

- Male
- Female

Here the same analysis methodologies as the primary and secondary analyses will be applied for the ITT populations (See Section 5.1.1.1.3, CFB ANCOVA). ANCOVA will be performed for each subgroup if the sample size available is at least 14 subjects. The Wilcoxon signed-rank test will be used when the one-sample t-test is not valid (See Section 5.1.1.1.3, CFB one -sample t-test).

Additionally, analysis of other important subgroups may be provided as appropriate.

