5.2.2 Changes to Analyses Prior to Database Lock

Version	Date	Summary
1.0	24 Oct 2017	Original version
2.0	28 Mar 2022	 Exact (Clopper-Pearson) 95% CI, Exact unconditional 95% CI using the score statistic, and Cochran-Mantel-Haenszel (CMH) was added in Table 5-2 to analyze binary urodynamic variable (Presence (versus total absence) of involuntary detrusor contractions at > 15 cm H2O)
		 CFB Mixed Model was deleted from Table 5-2. All CFB Mixed model analyses have been replaced with CFB ANCOVA as reflected in Table 5-12
		 Study part was removed as a factor from the CFB ANCOVA models
		 Details of how urodynamic assessments will be analyzed have been added in Table 5-12
		 Section 5.1.1.2 was modified to clarify analysis populations presented in demographics tables.
		 Exact Kolmogorov-Smirnov test was added in Table 5-2 to compare whether distributions of efficacy endpoints between patients treated with oxybutynin chloride gel in the two parts (Pre-Amendment 3 and Post-Amendment 3) of the study are the same
		 Section 5.1.1.3.1 was modified to provide details on how efficacy endpoints will be analyzed based on whether the distributions of efficacy endpoints between patients treated with oxybutynin chloride gel in the two parts (Pre- Amendment 3 and Post-Amendment 3) of the study were the same or not
		 Updated Table 5-15 definition of treatment-emergent adverse events in double-blind period to distinguish between participants who enter the 8-week open-label period from those that do not

6. Data Handling and Analysis Conventions

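### A non-significant Kolmogorov-Smirnov test makes a pooled gel-versus-placebo comparison primary, mixing unrandomised open-label gel patients into the randomised gel arm with no study-part term

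*SAP*

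**What the plan says.** SAP 5.1.1.3.1 first compares the primary endpoint between gel patients in the Pre-Amendment 3 double-blind period and gel patients in the Post-Amendment 3 open-label period. It uses an exact two-sample KS test, "with a p-value of 0.05 used as the threshold to reject the null hypothesis that the distributions for the two periods are the same".

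- **p ≥ 0.05:** the primary analysis is gel versus placebo in the Combined ITT population, by ANCOVA with baseline "as the covariate and treatment group (active or placebo) as the factor".
- **p < 0.05:** the parts are analysed separately, by ANCOVA against placebo for Pre-Amendment 3 and a one-sample t-test for Post-Amendment 3.
- **Either way:** "The analysis method which is not used as the primary analysis will serve as a supplementary analysis of the primary endpoint".

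The same gate applies to each secondary endpoint: "the main analysis will use the combined ITT population if" the KS p-value is at least 0.05. In practice it can act on two of the three, because Table 5-12 restricts the third: "Average volume of urine collected per catheterization (for Pre-Amendment 3 population only)".

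SAP 5.2.2 records, for version 2.0 of 28 March 2022: "Study part was removed as a factor from the CFB ANCOVA models".

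Protocol Amendment 4 (31 October 2022) is later but does not settle the matter. Section 11.5.1 specifies an ANCOVA with treatment group "and study part (Pre-Amendment 3 and Post-Amendment 3) as factors", then adds its own rule to separate the parts if heterogeneity is found. Section 11.2 labels the Combined ITT population primary in its list, then names the two separate ITT populations as primary in the text. The synopsis pools gel from both parts with baseline and treatment only.

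**The concern.** Every placebo patient was randomised, blinded and aged 6 to under 17. Every patient added by pooling is unrandomised, open-label, on gel and aged 3 to under 17 (Protocol 9.1, 9.4.3, 9.4.5). The documents show several ways in which the parts could differ in outcome:

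- The endpoint comes from a diary kept by the patient or caregiver, who is blinded in one part and not in the other.
- The age range is wider Post-Amendment 3, with efforts to enrol children aged 3 to under 6, a group with no placebo patients.
- Pre-Amendment 3 has a scheduled Week 2 diary that LOCF can carry forward. Post-Amendment 3 has no scheduled post-baseline diary before Week 6.

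The gate reads failure to reject as similarity. With study part out of the model, nothing but the baseline covariate separates a drug effect from a part effect. If open-label patients report more improvement, the claim is inflated; if less, the drug is understated. The analysis carrying the primary efficacy claim is thus chosen by a test with limited power to detect the problem it is meant to detect.

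The age subgroups in SAP 5.1.1.6 ("ANCOVA will be performed for each subgroup if the sample size available is at least 14 subjects") do not help. They leave the primary estimate unchanged, and the Combined ITT still mixes the parts within 6 to under 12 and 12 to under 17.

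**Working it through.** **Inputs from the plan** (SAP 5.1.2): SD of change 28; gel mean 25, placebo mean 5, difference 20; 48 per randomised arm; at least 25 open-label patients. KS threshold 0.05 (SAP 5.1.1.3.1). **Assumed:** two-sided alpha 0.05, inferred from the 95% intervals; 10, 20 or 48 randomised per arm, because actual enrolment is not given; a mean difference between parts (shift) of 0, ±10 or +20 points.

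**1. The plan's own power.** Normal approximation Φ(20/(28√(2/n)) − 1.96):
- n = 48: standard error 5.72; Φ(3.50 − 1.96) = 93.8%, against 93% stated.
- n = 43 (10% dropout): standard error 6.04; Φ(3.31 − 1.96) = 91.2%, against 90% stated (90.6% with the t distribution).

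The stated power is sound, but it describes the randomised comparison only.

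**2. Weight of the open-label patients in the pooled gel mean.** w = 25/(n + 25): 25/35 = 71%, 25/45 = 56%, 25/73 = 34%. A shift d that baseline does not explain moves the pooled contrast by about w·d.

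**3. KS cut-offs.** Exact critical distance D for n versus 25: 0.500, 0.400 and 0.3217, with exact p of 0.040, 0.043 and just under 0.050.

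**4. Simulation of the whole SAP rule.** Normal changes with SD 28; placebo mean 5; randomised gel mean 5 (null) or 25 (planned effect); open-label mean equal to randomised gel mean plus shift; baseline correlation 0. Pooled ANCOVA without study part if KS does not reject, otherwise the randomised ANCOVA. 40,000 trials per null cell, 24,000 per power cell. Error is the upper-tail rate, nominal 2.5%. Entries are for 10/20/48 per arm.

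| Shift, no drug effect | Pooled in (%) | Bias when pooled (points) | Upper-tail error (%) |
|---|---|---|---|
| 0 | – | – | 2.7–2.8 |
| +10 | 89/85/77 | +7.1/+5.6/+3.5 | 8.8/9.0/7.4 |
| +20 | 67/50/30 | +14.3/+11.1/+6.8 | 17.6/14.6/8.2 |
| −10 | – | −7.1/−5.5/−3.5 | about 1.6 |

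- With baseline correlation −0.4, the error is 10.0/9.7/7.8% at +10 and 20.0/16.7/9.3% at +20.
- At −10 the excess moves to the lower tail, which is 7–9%.
- Counting both tails (nominal 5%, 4,000 trials per cell), the SAP rule rejects in 9.7/10.6/8.0% at +10 and 19.6/16.4/10.5% at +20.
- The randomised ANCOVA and the ANCOVA with study part stay at 2.4–2.7% upper-tail error in every cell. Their estimates correlate 0.98/0.99/1.00, because placebo exists only in the randomised part.

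**5. Power at a true effect of 20 points.**

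| Shift | SAP rule (%) | Randomised ANCOVA (%) |
|---|---|---|
| 0 | 48/73/96 | 31/58/93 |
| −10 | 28/52/90 | 32/58/93 |

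**6. Standard errors.** Randomised: 28√(2/n) = 12.5, 8.9, 5.7. Pooled: 28√(1/n + 1/(n + 25)) = 10.0, 7.5, 5.2.

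**The case against.** The rule is fixed before database lock and the model changes are disclosed. The randomised ANCOVA is always reported; only its label changes. Baseline adjustment absorbs part of some differences, and large shifts tend to trigger separation: at 48 per arm, the only documented size, a 20-point shift leads to separation in 70% of trials. The largest errors come from assumed smaller arms, and the shifts are assumed too. The simulation uses continuous normal data, whereas the endpoint is a bounded percentage from a 2-day diary, where ties and ceilings are likely. Pooling also buys real power if the parts do not differ, and the later protocol synopsis itself pools without study part. Finally, the heterogeneity switch in Protocol 11.5.1 is not comparable to the SAP gate: its primary model contains study part, so the placebo contrast already rests on randomised patients whichever way the switch goes.

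What stands: the sizes are illustrative, the power cost is genuine, the 11.5.1 switch barely affects the placebo contrast, and the 11.2 and synopsis conflicts are consistency matters rather than the core defect. What does not: prespecifying a rule does not remove confounding, and a supplementary analysis does not carry the claim. Even at 48 per arm, a shift equal to the whole planned effect is still pooled in 30% of trials.

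**Conclusion.** The concern holds and should be fixed before database lock. The SAP rule treats a non-significant KS test as proof of similarity and then lets a difference between parts into the placebo contrast with weight 34% to 71%, for 48 down to 10 randomised per arm. Upper-tail error is about 7% to 9% at a 10-point shift and 8% to 18% at a 20-point shift, against 2.5%; with a negative shift, power falls below that of the randomised comparison. These figures rest on SD 28, 25 open-label patients, normal outcomes and assumed shifts and arm sizes. Error is near nominal only if the parts do not differ, and the documents give neither the size nor the direction of any difference. The direction of the argument does not depend on the decimals.

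**What to change.** **SAP 5.1.1.3.1.** Delete the KS gate for the primary endpoint, first-morning volume and number of catheterizations. State that the primary placebo comparison is the Pre-Amendment 3 ITT ANCOVA (baseline covariate, treatment factor), whatever any comparison between parts shows. Report Post-Amendment 3 as a single-arm mean change with 95% CI. Keep the Combined ITT model without study part as a labelled supplementary analysis, preferably limited to ages 6 to under 17. Restoring study part as a fixed factor, as in Protocol 11.5.1, would give nearly the same contrast. Making the randomised ANCOVA primary matches the Pre-Amendment 3 objective and the comparison that the stated 93% power describes.

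**Protocol.** Name one primary population in 11.2, align the synopsis, and remove the heterogeneity switch in 11.5.1 so that both documents state one unconditional primary analysis.

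**Cost.** Wording only; no new data, and the analysis is already in the SAP. The price is the wider standard error and, if the parts truly do not differ, the loss of power shown above: 17, 15 and 3 percentage points at 10, 20 and 48 per arm. That extra power is available only by assuming the parts are exchangeable, which the gate cannot establish.

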4.1 Study Design Summary

This study was initiated as a double-blind, placebo-controlled study with an open-label extension and was amended via protocol amendment (Protocol Amendment 3) to enroll participants under only open-label treatment. Therefore, analyses are described with respect to prior to protocol amendment 3 ("pre-amendment 3") and with protocol amendment 3 ("post-amendment 3").

Prior to Amendment 3, participants aged 6 years to < 17 years who had a diagnosis of detrusor overactivity associated with a neurological condition and were using clean intermittent catheterization (CIC) to control bladder function were randomly assigned 1:1 to receive doubleblind oxybutynin chloride gel or placebo gel for 6 weeks. Enrollment was stratified based on sex, age, and weight. Stratification was done within the following groups: male and female; 6 to < 12 years-of-age and 12 to < 17 years-of-age; and by weight category: ≤ 25.0 kg and > 25.0 kg for the 6 to < 12 years-of-age group and \le 50.0 kg and > 50.0 kg for the 12 to < 17 years-of age group. Enrollment into the 6-week treatment period was to be followed by an open-label, 8-week period to generate safety data. All participants began treatment with 0.75 g of gel/day for 2 weeks. Participants then returned to the clinic at Week 2 for a potential dose titration and at this time their dose could have been adjusted up to 1 g/day, down to 0.5 g/day, or remained the same at 0.75 g/day. The determination of dose was based on the investigator's clinical judgment and assessment of the patient's bladder symptoms and treatment side effects. Dose titration was permitted only once during the entire 6-week double-blind, placebo-controlled period. Participants continued blinded treatment for 4 additional weeks until the end of the double-blind treatment period.

Post-Amendment 3, the study became a multicenter, open-label, dose-titration study in pediatric participants, ages 3 years to < 17 years, with detrusor overactivity associated with a neurological condition. A minimum of 25 participants are to be enrolled. Efforts will be made to enroll a greater number of participants from the ages of 3 years to < 6 years. Participants must be suitable

[figure not shown]

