	values at an analysis visit (e.g., Week 6 LOCF)
	 Estimates derived from a model for CFB value controlling for factors (treatment
	group) and covariates (baseline value)
	Least squares (LS) means and standard errors
	LS mean differences, and 95% confidence intervals for oxybutynin chloride
	gel vs Placebo
	 P-values from contrast t-test comparing oxybutynin chloride gel vs Placebo
	N1 = portioinants with non-missing values at both baseline and the specific 1
	• N1 = participants with non-missing values at both baseline and the specified postbaseline analysis visit
Exact (Clopper-	Exact 95% CI for a single proportion
Pearson) 95% CI	Exact 9370 CI for a single proportion
1 carson, 75/0 Cl	

SAP OG09002 Oxybutynin Chloride 10% Gel

Methodology	Description
Exact	• Exact 95% CI for difference between two proportions
unconditional 95%	
CI using the score	
statistic	
Cochran-Mantel-	P-value from CMH test controlling for baseline covariates
Haenszel (CMH)	
Kolmogorov-	P-value from exact Kolmogorov-Smirnov test to examine whether two distributions
Smirnov test	are the same

CFB = change from baseline; ANCOVA = analysis of covariance.

Raw and derived data listings will be provided, and will be fully defined in the table, figure, and data listing specification document.

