5.1.2 Determination of Sample Size

Sample size was calculated for the protocol as originally designed (Pre-Amendment 3: double-blind, placebo-controlled treatment period followed by an open-label extension) as follows:

This study was planned to include a minimum of 96 pediatric participants aged 6 to < 17 years who have a diagnosis of detrusor overactivity associated with a neurological condition. The sample size was selected to provide an adequate number of participants to evaluate the safety and efficacy of oxybutynin chloride gel treatment in a pediatric population. Participants were randomized in a 1:1 fashion to oxybutynin chloride gel or placebo within each stratification level, which were based on age, weight, and sex. Estimates for the average change from baseline (CFB) in the percentage of catheterizations without a leaking accident as well as the standard deviation for this variable were taken from oxybutynin TDS in Study O03010. Assuming a common standard deviation of 28 for the CFB in the percentage of catheterizations without a leaking accident, a difference between treatment groups of 20 (assuming average for oxybutynin chloride gel = 25 and average for placebo = 5), and n = 48 participants per treatment group, there is 93% power to detect a statistically significant difference between treatment groups. Based on discontinuation rates from Study O03010, if we assume a 10% dropout rate, then there is 90% power to detect a statistically significant difference between treatment groups.

The open-label study (participants enrolled Post-Amendment 3) will include a minimum of 25 pediatric participants aged 3 to < 17 years (efforts will be made to enroll a greater number of participants aged 3 years to < 6 years) who have a diagnosis of detrusor overactivity associated with a neurological condition. This sample size is expected to provide a minimum of 10 participants with 14 weeks of exposure.

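### Pre-Amendment 3 randomisation was stratified by sex, age and weight, but the Pre-Amendment 3 ANCOVA adjusts for baseline only: a valid test, conservative if the strata are prognostic

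*SAP*

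**What the plan says.** SAP 4.1 states that "Enrollment was stratified based on sex, age, and weight", with levels "male and female; 6 to < 12 years-of-age and 12 to < 17 years-of-age" and a weight cut within each age group (25 kg for the younger, 50 kg for the older). That makes 2 × 2 × 2 = 8 strata. Protocol 9.4.3 gives the same scheme, and SAP 5.1.2 confirms that patients were "randomized in a 1:1 fashion to oxybutynin chloride gel or placebo within each stratification level, which were based on age, weight, and sex".

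The Pre-Amendment 3 primary analysis in SAP 5.1.1.3.1 compares gel with placebo "using an ANCOVA model with the baseline measure of the primary variable as the covariate and treatment group as the factor". Table 5-2 (SAP 5.1.1.1.3) defines the CFB ANCOVA in the same way, with treatment group as the only factor and the baseline value as the only covariate. Table 5-12 applies this model to the primary, secondary and continuous urodynamic endpoints. For the binary urodynamic endpoint, Table 5-2 describes the method as "P-value from CMH test controlling for baseline covariates" and does not name the covariates.

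Protocol 11.5.1 specifies the same baseline-and-treatment ANCOVA for the Pre-Amendment 3 population. It also had a mixed model for the combined data, of which it says "The model will include the baseline measure and other baseline characteristics as covariates". SAP version 2.0 deleted that model (SAP 5.2.2). Sex, age and weight now enter the efficacy analysis only as subgroups (SAP 5.1.1.6). No reason is given for leaving the strata out of the model.

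**The concern.** Stratified randomisation balances the arms within each stratum, so differences between strata largely cancel out of the treatment contrast. A model without the strata does not recognise this: the between-stratum variation stays in the residual error. If the strata are prognostic given baseline, the model standard error exceeds the true sampling standard deviation of the estimate. Confidence intervals are then too wide, the test rejects too rarely under the null, and some power is lost. Subgroup analyses do not repair this, because they do not adjust the overall comparison.

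This ANCOVA is the only randomised comparison with placebo. It is primary if the Kolmogorov-Smirnov test gives p < 0.05 and supplementary otherwise, so it is reported either way.

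The point is limited to the randomised Pre-Amendment 3 comparison. In the Combined ITT ANCOVA the added patients are all on gel, unrandomised and unstratified. Omitting age, weight and study part there is a separate confounding question of unknown direction.

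**Working it through.** **Inputs from the documents.** SAP 5.1.2: SD of the change from baseline 28, difference 20 (25 against 5), 48 per arm, 10% dropout, stated power 93% and 90% after dropout. A two-sided 5% level is inferred from the two-sided 95% intervals in SAP 5.1.1.1.3, since no alpha is stated with the sample size.

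**Assumptions not in the documents.** The share R² of the residual variance (given baseline) that the strata explain; the number actually randomised before Amendment 3; block size 4; eight equally likely strata; residual SD 28 given baseline.

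**Reproducing the plan's power.** SE = 28 × √(2/n).
- n = 48: SE = 5.72, and the two-sample t-test has power 93.4% (stated 93%).
- n = 43 (96 less 10% is about 86): SE = 6.04, power 90.6% (stated 90%).

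**Large-sample approximation.** With strata balanced by design, the true variance of the estimate is about (1 − R²) times the variance the baseline-only model reports. Hence:
- True type I error ≈ 2 × [1 − Φ(1.96/√(1 − R²))], which gives 5.0, 4.4, 3.9, 2.8 and 1.9% for R² = 0, 0.05, 0.10, 0.20 and 0.30.
- Power of the planned model ≈ Φ[(20/SE − 1.96)/√(1 − R²)], and with strata ≈ Φ[20/(SE × √(1 − R²)) − 1.96]. At SE = 6.04, 20/SE = 3.312. For R² = 0.10 these are Φ(1.352/0.9487) = 92.3% and Φ(3.491 − 1.96) = 93.7%. For R² = 0.20 they are Φ(1.352/0.8944) = 93.5% and Φ(3.703 − 1.96) = 95.9%.

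**Simulation of the proposed model.** 10,000 trials per setting, additive stratum effects with half their variance from sex and half from age-by-weight. The planned model (treatment and baseline) is compared with the same model plus sex (1 df) and age-by-weight (3 df). For 86 analysed, 96 were randomised and 10 dropped at random; the smaller sizes have no dropout. Monte Carlo error is about 0.2 points for type I error and 0.3 to 0.5 points for power.

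| Analysed N | R² | Power, planned | Power, with strata |
|---|---|---|---|
| 86 | 0 | 90.4% | 90.2% |
| 86 | 0.10 | 90.9% | 92.6% |
| 86 | 0.20 | 91.5% | 94.8% |
| 40 (assumed) | 0 | 57.6% | 56.2% |
| 40 (assumed) | 0.10 | 59.1% | 62.2% |
| 40 (assumed) | 0.20 | 58.1% | 65.6% |
| 30 (assumed) | 0 | 45.4% | 43.2% |
| 30 (assumed) | 0.10 | 44.2% | 46.5% |
| 30 (assumed) | 0.20 | 44.9% | 51.5% |

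At N = 86 the planned model's type I error was 5.2, 4.2 and 3.2% for R² = 0, 0.10 and 0.20. Its mean reported SE was 6.07 at R² = 0.10 and 0.20, against a true SD of its estimate of 5.86 and 5.54. The adjusted model's mean SE was 5.78 and 5.45. Intervals under the planned model are therefore 6.07/5.78 = 1.05 and 6.07/5.45 = 1.11 times as wide.

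**Checks with separate simulations.**
- At N = 86, a second run gave planned against adjusted power of 90.2 and 89.7%, 91.5 and 93.2%, and 92.7 and 95.5% for R² = 0, 0.10 and 0.20, with planned-model type I error of 4.7, 3.7 and 3.0%.
- At N = 96, fitting all eight strata (8,000 trials), planned-model type I error fell from 5.1% at R² = 0 to 2.3% at R² = 0.30, while the adjusted model stayed between 4.6 and 5.3%. Power at R² = 0.30 was 95.6 against 98.3%.
- At N = 40, fitting all eight strata cost 2.9 points at R² = 0 (58.1 against 55.2%), more than the 1.4 points for the four-df form (57.6 against 56.2%).

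**The case against.** The strongest reply is that nothing is broken. The SAP keeps the protocol's own Pre-Amendment 3 model, the test is valid, and power stays at or above the stated 90% in every planned-size scenario. The benefit rests on an R² that the documents do not give. All of that is right, and it is why this is an efficiency point.

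Four further objections carry weight.
- **Residual SD.** The 28 in SAP 5.1.2 is the SD of the change from baseline, not the residual SD given baseline. If baseline explained 25% of the variance (an assumption), the residual SD would be 28 × √0.75 = 24.25. Simulated power at N = 86 (6,000 trials) is then 96.4 against 96.4%, 97.2 against 97.7%, and 97.6 against 98.6% for R² = 0, 0.10 and 0.20. The power gain shrinks to about 1 point, but the excess in the standard error remains.
- **Small samples.** The achieved Pre-Amendment 3 enrolment is unknown. At an assumed N = 20 with R² = 0, one simulation gave 31.3 against 27.4% and another a loss of about 3 points. A loss of about 2 points is therefore the worst case only for sizes down to 30.
- **Mixed model.** The deleted model was for the combined data and its extra covariates were unnamed. Its removal took no stratification factor out of the randomised comparison.
- **CMH wording.** The phrase does not exclude the strata. It is a lack of specification rather than an omission.

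None of this supplies a reason for leaving the design factors out of the randomised comparison.

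**Conclusion.** The concern holds as an efficiency point. The Pre-Amendment 3 ANCOVA omits the factors used to stratify randomisation. It remains unbiased, with type I error at or below nominal, and becomes conservative to the extent that the strata are prognostic beyond baseline.

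At the planned size, with R² from 0 to 0.20 and residual SD 28, adding the strata changes power by between about −0.2 and +3 points and removes an excess interval width of 0 to 11%. The direction is certain only if the strata matter: with non-prognostic strata, adjustment costs about 1 to 2 points at N = 40 to 30 and 3 to 4 points at N = 20. R² and the achieved enrolment are both assumed. The change is worth making, but the validity of the planned test does not depend on it.

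**What to change.** Before database lock and unblinding:

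1. In SAP Table 5-2 and section 5.1.1.3.1, add sex and the four-level age-by-weight category as fixed effects to the Pre-Amendment 3 CFB ANCOVA for the primary, secondary and continuous urodynamic endpoints. Main effects (4 df) are preferable to all eight strata (7 df) if the sample is small.
2. Name the same factors in the Pre-Amendment 3 CMH test, with a pre-stated rule for collapsing sparse strata. Eight strata average about 11 patients each at N = 86 (86/8) and 5 at N = 40 (40/8).
3. Keep the baseline-only model as a sensitivity analysis.
4. If the strata are left out, state why. A very small Pre-Amendment 3 sample would be a defensible reason, and the sponsor can judge it from the blinded enrolment count.

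The cost is SAP wording and programming only, since the variables are already collected. The statistical cost is 4 degrees of freedom: about 0.2 points of power at N = 86 if the strata are not prognostic, rising in small samples as given above.
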